X-rays should be sent out to the core laboratory for evaluation within five business days. The core laboratory will review the x-rays for quality and the presence of stent fracture. The core laboratory will communicate to the investigational site within seven business days after receiving the x-rays if the image quality is inadequate to make an assessment of stent fracture and will also provide guidance on specific measures for the site to take in order to adequately assess for stent fracture. If the image quality of the x-ray is inadequate to make an assessment of stent fracture, the investigational site must request that the subject return for a second series of x-rays.

Study coordinators will be trained on the quality assessment measures used for x-ray acquisition for stent fracture assessment. It is recommended that the study coordinators be present at the time of the x-ray acquisition to provide direction and guidance to the x-ray personnel. Each site must review x-rays for image quality prior to sending to core lab.

Table 6 lists the 1-year follow-up assessment requirements.

1-Year Follow-up Requirements	Follow-up Window
Clinical status by Rutherford Clinical Category	
Ankle-brachial index	
Walking Impairment Questionnaire	1-Year Visit:
X-ray	335-395 Days Post-Procedure
Adverse event documentation	
Primary Endpoint Assessments: Amputation, Death,	
Clinically Driven Target Lesion Revascularization	

 Table 6: 1-Year Follow-up Assessment Requirements

2-Year and 3-Year Follow-Up Requirements

All subjects are required to have follow-up visits at 2 and 3 years. Ankle-brachial index Walking Impairment Questionnaire, and an evaluation for AEs will be completed and documented at each visit. X-ray imaging to identify stent fracture is also required. Refer to the Manual of Operations for the x-ray imaging and transmission requirements.

X-rays should be sent out to the core laboratory for evaluation within five business days. The core laboratory will review the x-rays for quality and the presence of stent fracture. The core laboratory will communicate to the investigational site within seven business days after receiving the x-rays if the image quality is inadequate to make an assessment of stent fracture and will also provide guidance on specific measures for the site to take in order to adequately assess for stent fracture. If the image quality of the x-ray is inadequate to make an assessment of stent fracture, the investigational site must request that the subject return for a second series of x-rays.

Study coordinators will be trained on the quality assessment measures used for x-ray acquisition for stent fracture assessment. It is recommended that the study coordinators be

present at the time of the x-ray acquisition to provide direction and guidance to the x-ray personnel. Each site must review x-rays for image quality prior to sending to core lab.

Table 7 lists the 2-year and 3-year follow-up assessment requirements.

 Table 7: 2-Year and 3-Year Follow-up Assessment Requirements

2-Year and 3-Year Follow-up Requirements	Follow-up Window
Ankle-brachial index	
Walking Impairment Questionnaire	2-Year Visit: 685-775 Davs Post-Procedure
X-ray	
Adverse event documentation	3-Year Visit:
Primary Endpoint Assessments: Amputation,	1050-1140 Days Fost-Flocedure
Death, Clinically Driven Target Lesion	
Revascularization	

All-cause mortality at 1, 2 and 3 years will be reported.

Unscheduled Assessments During Follow-up

Performance of study assessments at other follow up visits should be done as clinically indicated and corresponding data must be documented and submitted to the sponsor.

If a subject is clinically indicated for a re-intervention of the target vessel, a resting ABI, xray evaluation for stent fracture and angiogram are to be performed and documented prior to the endovascular procedure. If possible, all non-invasive assessments should be captured for the study, including ABI, and x-ray evaluation, even if the re-intervention and angiogram are declined. If the subject does not want to undergo an angiogram, re-intervention, or noninvasive assessments it will not be considered a deviation from the clinical protocol. In the event a subject declines to proceed with an angiogram, re-intervention, or non-invasive testing, the reason will be documented in the subject's medical record.

Termination of Participation

All subjects have the right to terminate themselves from participation at any point during the study. In addition, Principal Investigators also have the ability to terminate subject participation in the study (see page 26, "Subject Withdrawal" for rationale for physician-directed withdrawal). A description of the reason for their termination will be documented. Reasons for termination include: completion of study, subject withdrawal, physician-directed subject withdrawal, lost-to-follow-up, and death.

Loss to Follow-Up

Every attempt must be made to have all subjects complete the follow up visit schedule. A subject will not be considered lost-to-follow-up unless efforts to obtain compliance are unsuccessful. At a minimum, the effort to obtain follow-up information must include three attempts to make contact via telephone and if contact via phone is not successful, then a certified letter from the Principal Investigator must be sent to the subject's last known address. Both telephone and letter contact efforts to obtain follow up must be documented in both the subject's medical records and on the study case report forms (CRFs).

Subject Withdrawal

All study subjects have the right to withdraw their consent at any time during the study. Whenever possible, the site staff should obtain written documentation from the subject that wishes to withdraw his/her consent for future follow-up visits and contact. If the site staff is unable to obtain written documentation, all information regarding the subject's withdrawal must be recorded in the subject's medical record. In addition, the appropriate CRFs must be completed for the subject and clear documentation of the subject's withdrawal be provided to the sponsor.

Withdrawal of a subject from the study can occur at the direction of the Principal Investigator or the sponsor. Acceptable reasons for physician-directed subject withdrawal are; the subject is not adhering to the protocol requirements, the subject has enrolled in another study that conflicts with the DURABILITY PAS primary endpoint, or if the physician deems it in the best interest for the safety or welfare of the subject to withdraw.

Deviations to the Investigation

Principal Investigators and site staffs must avoid all protocol deviations. Use of any devices other than PTA balloons for recanalization (e.g. cutting balloon, scoring balloon, thrombectomy, atherectomy, brachytherapy or laser devices) during the index procedure will be considered a deviation of the clinical protocol. Use of embolic protection devices during the index procedure will also be considered a deviation of the clinical protocol. Only the use of PTA balloons, guidewires, and devices to facilitate placement of a guidewire distal to the target lesion (e.g. Cordis Frontrunner® CTO Re-Entry Catheter, the Cordis Outback® LTD™ Re-Entry Catheter, and the Kensey Nash Safe-Cross® System) during the index procedure will not be considered a deviation of the clinical protocol. The sponsor will not make any exceptions to the protocol and will not provide waivers to subjects with any protocol deviations. Any emergency deviations (deviations from the protocol to protect the life or physical well being of a subject; e.g. use of a device not approved for use in the superficial femoral artery) that occur must be reported to the sponsor and the site IRB per their guidelines.

While this clinical protocol is designed to study the safety and effectiveness of the EverFlex device in subjects who received only one stent, the sponsor recognizes there may be circumstances necessitating the need to implant more than one stent in the superficial femoral artery during the index procedure. Implantation of a second stent in the SFA during the

index procedure is not considered a protocol deviation. The sponsor will track and report all instances when more than one stent is implanted in the SFA during the index procedure, including information on the reason(s) why the additional stent was needed, as well as the investigator and site.

Device Malfunctions

A device malfunction occurs in any case when the device does not perform in its intended function when used in accordance with the *Instructions for Use*. All device malfunctions must be reported to the sponsor.

If a device malfunction results in an adverse event for the subject, this adverse event will be considered a reportable adverse event and must be reported as an adverse event. Device malfunctions that do not result in an adverse event for the subject do not need to be recorded as an AE, as they are not considered an AE.

If a device malfunction occurs with the EverFlex device, return the device to ev3, following the procedure outlined in the Regulatory Binder.

Adverse Events

The following adverse events, as defined below, will be reported in this study.

Procedural Adverse Events (AEs) are defined as any event, regardless of severity, that occurs during the index procedure through the pre-discharge visit. The sponsor should be notified in a timely manner. If the Procedural AE is determined to be an SAE, follow reporting guidelines for SAEs below.

Major Adverse Events (MAEs) are defined as: clinically-driven target lesion revascularization, amputation of treated limb, and all-cause mortality. All MAEs should be reported as soon as possible after the investigational site's knowledge of the event. A written report will be provided to the sponsor within 10 business days after the investigator learns of an MAE and must be provided to the IRB according to the board's reporting guidelines.

Serious Adverse Events (SAEs) are any adverse events that result in death, are life threatening, require inpatient hospitalization greater than 24 hours, or prolongation of an existing hospitalization, require intervention to prevent permanent impairment/damage, or result in persistent or significant disability/incapacity. A written report will be provided to the sponsor within 10 business days after the investigator learns of an SAE and must be provided to the IRB according to the board's reporting guidelines.

An Unanticipated Adverse Device Effect (UADE) is defined as any serious adverse experience (event) leading to injury, illness, or death of a subject not previously identified in nature, severity or degree of incidence in the protocol that may be directly related to the use of the device.

In the event of a UADE the investigational site will inform the sponsor and IRB as soon as possible. A written report will be provided to the sponsor within 10 business days after the investigator learns an unanticipated adverse device effect and will be provided to the IRB according to the board's reporting guidelines.

Deaths

Each subject death must be reported to the sponsor. A death must be reported to the sponsor as soon as possible after the site's knowledge of the event. A written report will be provided to the sponsor within 10 business days after the investigator learns of a death and will be provided to the IRB according to the board's reporting guidelines. It is requested that a copy of the death certificate and a copy of the autopsy report, if applicable, be sent to the sponsor when available. Any other source documents related to the death should also be provided to the sponsor. In the event that no source documents are available the PI will be required to submit a letter to the sponsor describing the circumstances of the subject's death.

Core Laboratory Requirements

Angiographic Core Laboratory

An independent Angiographic Core Laboratory will review all scheduled and unscheduled angiographic procedure data. See Angiographic Core Laboratory Procedures in the Manual of Operations.

The Angiographic Core Laboratory is:

[name] Medical Director Beth Israel Deaconess Medical Center Angiographic Core Laboratory [name] [contact] [contact]

X-ray Core Laboratory

An independent x-ray Core Laboratory will review all scheduled and unscheduled x-ray data. See X-ray Core Laboratory Procedures in the Manual of Operations.

The X-ray Core Laboratory is:

[name] Medical Director Beth Israel Deaconess Medical Center Angiographic Core Laboratory [name] [contact] [contact] X-rays should be sent out to the core laboratory for evaluation within two to five business days. The core laboratory will review the x-rays for quality and the presence of stent fracture using the "Stent Location and Integrity Grid". The core laboratory will communicate to the investigational site within seven business days after receiving the x-rays if the image quality is inadequate to make an assessment of stent fracture and will also provide guidance on specific measures for the site to take in order to adequately assess for stent fracture. If the image quality of the x-ray is inadequate to make an assessment of stent fracture, the investigational site must request that the subject return for a second series of x-rays.

There will be a Stent Fracture Adjudication Committee formed to adjudicate the classification and categorization of stent fractures. Clinical summaries describing baseline demographic information, physical findings, medical history and clinical symptomatology will be prepared for the Stent Fracture Adjudication Committee.

Clinical Events Committee

An independent Clinical Events Committee (CEC) will be established. The CEC will consist of physicians who are not investigators in the study and who do not have any significant investment in ev3 or any of their entities. The committee will include, but not be limited to, the specialties of interventional cardiology, vascular surgery, and interventional radiology.

The CEC is responsible for conducting a review of all adverse events, including SAEs and MAEs, reported for study subjects in the study. The CEC will adjudicate and classify all primary and secondary endpoint events as defined in the clinical protocol. In addition, the CEC will be responsible for adjudicating and classifying any site reported device-related, procedure-related or study requirement-related adverse events. The CEC will determine if any device-related adverse event is an unanticipated adverse device effect.

Case Report Forms

Electronic case report forms (eCRFs) will be used to collect study data. The eCRFs will be electronically viewed and signed by the Principal Investigator. All appropriate sections of the eCRFs must be completed.

Case report forms related to the index procedure should be completed within two weeks following subject discharge. The follow-up forms must be completed in a timely manner after the follow-up visit.

Study monitors designated by the sponsor will review the information documented in the eCRFs and verify the information recorded is consistent with medical records and other source documents. Errors or incomplete entries will be rectified.

The sponsor will use the study data for statistical and tracking purposes and will treat the information as confidential. A representative of the FDA may review or copy study records during an audit.

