5.0 STATISTICAL METHODS

Primary Endpoint and Sample Size Adjustment

Hypothesis Testing

The study's primary endpoint has been previously defined. The associated statistical hypothesis is that the resulting event-free rate at 36 months is greater than the Performance Goal (PG), which is adapted from RESILIENT 3-year data on freedom from TLR for PTA subjects.

The null and alternative hypotheses for the primary endpoint are:

H ₀ :	$\pi_t \leq \pi_{pg}$

Ha: $\pi_t > \pi_{pg}$

where π_t is the event-free rate in subjects treated with an EverFlex device and π_{pg} is the PG of 35%.

Analysis of this endpoint will be carried out by Kaplan-Meier methods. The point estimate of the event-free rate at 36 months (1095 days) from the date of the index procedure will be computed along with its one-sided 97.5% lower confidence bound. If the lower bound is greater than 35%, it will be declared that the PG and the corresponding primary study objective have been met.

Justification of Performance Goal

The structure of the composite endpoint is derived from a 12-month composite endpoint described by VIVA Physicians Inc. (VPI) as part of their development of safety and effectiveness Performance Goals (PG) for the use of bare nitinol stents in the treatment of femoropopliteal lesions.^{19, 20} The VPI 12-month composite was defined as acute death, index limb amputation and target vessel revascularization (TVR) through 12-months. This composite event rate in the studies reviewed was 30.5% at 12 months (Table 8). However, there were no long-term follow-up to 3 years reported.

	Company A	Company B	Company C	Combined
	(n=29)	(n=24)	(n=63)	(n=116)
12 month Composite (acute death, 12m TVR, 12m amputation	38.5% (10/26)	33.3% (6/18)	25.5% (13/51)	30.5% (20/95)

Table 8: PTA Performance	e Goals – Safety Data
--------------------------	-----------------------

Recently, 3-year data on freedom from TLR was presented on the PTA arm of the RESILIENT study.²¹ The reported event-free rate at 3 years among RESILIENT subjects randomized to PTA treatment was 41.8%, a value which is adjusted as follows to account for longer lesions enrolled in DURABILITY II.

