The statistical model employed is a Cox regression on the outcome of freedom from TLR applied to DURABILITY II data. Lesion length (in mm) as measured by the core laboratory was the predictor of outcome, resulting in a point estimate of 0.01543 for the logarithm of the hazard ratio, and therefore a hazard ratio of $e^{0.01543}$ =1.0155 per mm of lesion length (with longer lesions associated with lower freedom-from-TLR rates).

As the mean lesion length in RESILIENT was 68 mm versus 89 mm in DURABILITY II, the resulting adjusted event-free rate can be obtained using a formula analogous to adjusting with odds ratios:

 $\pi_{pg}/(1-\pi_{pg}) = (0.418/(1-0.418))^{*}1.0155^{(89-68)}$

Solving this equation gives $\pi_{pg} = 0.342$, which is rounded up to give the PG of 35%. Note that this PG is conservative in that it (1) does not attempt to account for any other systematic differences between RESILIENT and DURABILITY II and (2) does not explicitly account for the other elements of the composite endpoint (since these were not presented for RESILIENT), which if included would lower the expected freedom-from-event rate below that seen for TLR alone.

Potential Outcomes

Table 9 summarizes approximate outcomes under potential results for freedom from event, using binomial estimation. Note that the actual analysis will be conducted using time-to-event methods and is subject to currently unknown censoring times, and that therefore the actual success criteria will vary slightly from those noted below.

Table 9: Approximation to Possible Outcomes and Corresponding 97.5% LowerConfidence Bound

Primary Endpoint (PG=35%)			
Sample Size	Count of subjects with freedom from event	36-Month Freedom From Event Rate	97.5% lower confidence bound
108	48	44.4%	35.1%
108	49	45.4%	36.0%
108	50	46.3%	36.9%
108	51	47.2%	37.8%

Sample Size and Power

The required sample size for evaluating the primary endpoint can be approximated using the normal method for testing a single proportion (as above, under Kaplan-Meier methods the actual power will vary slightly from this calculation):

$$n = \frac{(\pi_{pg} \times (1 - \pi_{pg})) \times (Z_{1 - \alpha} + Z_{1 - \beta} \sqrt{\pi_t (1 - \pi_t) / (\pi_{pg} (1 - \pi_{pg})))^2}}{(\pi_t - \pi_{pg})^2}$$

Where,

- Type I error (α) = 0.025 (one-sided)
- Statistical power $(1 \beta) = 90\%$
- Z is the standard normal deviate for $\alpha = 0.025$ and $\beta = 0.10$.
- π_t is estimated freedom-from-event at 36 months
- π_{pg} is the PG

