Using this approximation with $\pi_t = 0.55$ (estimated from current DURABILITY II data), $\pi_{pg} = 0.35$ (the *a priori* performance goal), $Z_{1-\alpha} = 1.96$ and $Z_{1-\beta} = 1.28$ gives a sample size of 62. Allowing for approximately 30% of subjects lacking a 3-year follow-up visit, the needed sample size under this approximation for 90% power is a minimum of 89.

An additional sample size requirement is based on the secondary endpoint of freedom from stent fracture at 1 year. In DURABILITY I and DURABILITY II, 1-year stent fracture rates of 8.1% (n=151) and 0.4% (n=287), respectively, were observed. The pooled fracture rate of these two studies is 3.0% (13/438), around which a confidence interval of specified width is desired. The desired precision is 7.2% (half-width of 3.6%); we therefore find a 95% two-sided normal confidence interval with upper bound 3.0% + 3.6% = 6.6%, and extract the relevant sample size.

Sample Size for Freedom from Stent Fracture			
Sample Size	Count of subjects with event	Event Rate	97.5% upper confidence bound (95% two-sided)
95	3	3.16%	6.67%
96	3	3.13%	6.61%
97	3	3.09%	6.54%
98	3	3.06%	6.47%

	Table 10:	Sample Size	e Freedom from	Stent Fracture
--	-----------	-------------	----------------	----------------

From the above table, the required sample size at 1 year is 97 subjects. Considering a 10% rate of attrition, a minimum of 108 subjects are needed, which is larger than the sample size

of 89 calculated for the primary endpoint. The enrolled sample size is therefore 108. Please note that multiple stents are allowed in each subject in the study. The stent fracture endpoint will be analyzed on stent level. To be conservative, sample size calculation is performed on subject level. Therefore more stents than the above assumption may be included in the analysis.

Data Analysis Plan

All statistical analyses will be performed using Statistical Analysis System (SAS) for Windows (version 9.2 or above, SAS Institute Inc. Cary, N.C.) or other widely accepted statistical or graphical software. In general, data for all study subjects combined will be presented. Individual data will be presented in subject listings.

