$$n = \frac{(\pi_{pg} \times (1 - \pi_{pg})) \times (Z_{1-\alpha} + Z_{1-\beta} \sqrt{\pi_t(1 - \pi_t) / (\pi_{pg}(1 - \pi_{pg}))})^2}{(\pi_t - \pi_{pg})^2}$$

Where,

- Type I error (α) = 0.025 (one-sided)
- Statistical power ($1 - \beta$) = 90%
- Z is the standard normal deviate for $\alpha = 0.025$ and $\beta = 0.10$.
- π_t is estimated freedom-from-event at 36 months
- π_{pg} is the PG

Using this approximation with $\pi_t = 0.55$ (estimated from current DURABILITY II data), $\pi_{pg} = 0.35$ (the *a priori* performance goal), $Z_{1-\alpha} = 1.96$ and $Z_{1-\beta} = 1.28$ gives a sample size of 62. Allowing for approximately 30% of subjects lacking a 3-year follow-up visit, the needed sample size under this approximation for 90% power is a minimum of 89.

An additional sample size requirement is based on the secondary endpoint of freedom from stent fracture at 1 year. In DURABILITY I and DURABILITY II, 1-year stent fracture rates of 8.1% (n=151) and 0.4% (n=287), respectively, were observed. The pooled fracture rate of these two studies is 3.0% (13/438), around which a confidence interval of specified width is desired. The desired precision is 7.2%

(half-width of 3.6%); we therefore find a 95% two-sided normal confidence interval with upper bound $3.0\% + 3.6\% = 6.6\%$, and extract the relevant sample size.

Table 3: Sample Size Freedom from Stent Fracture

Sample Size for Freedom from Stent Fracture			
Sample Size	Count of subjects with event	Event Rate	97.5% upper confidence bound (95% two-sided)
95	3	3.16%	6.67%
96	3	3.13%	6.61%
97	3	3.09%	6.54%
98	3	3.06%	6.47%

From the above table, the required sample size at 1 year is 97 subjects. Considering a 10% rate of attrition, a minimum of 108 subjects are needed, which is larger than the sample size of 89 calculated for the primary endpoint. The enrolled sample size is therefore 108. Please note that multiple stents are allowed in each subject in the study. The stent fracture endpoint will be analyzed on stent level. To be conservative, sample size calculation is performed on subject level. Therefore, more stents than the above assumption may be included in the analysis.

7. Statistical Methods

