7.4 Handling of Missing Data and Dropouts

In general, imputation of missing data will not be performed for all analyses. Subjects who dropped out will be censored at date of last follow-up contact.

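### The minimum tracing effort for lost subjects includes no check for endpoint events, and no analysis tests the censoring that follows, so a primary result near the 35% goal would rest on an unexamined assumption

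*Protocol*

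**What the plan says.** **Tracing.** Protocol 4.0, Loss to Follow-Up, asks for every attempt to complete the visit schedule and then sets a floor: "the effort to obtain follow-up information must include three attempts to make contact via telephone and if contact via phone is not successful", a certified letter goes to the last known address. No search of site records, enquiry to the treating physician or vital-status check is named.

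**Event capture.** Protocol Tables 4 to 7 list the primary endpoint assessments at each visit. Separately, the Adverse Events and Deaths sections require target lesion revascularization (TLR), amputation and death to be reported once the site knows of them, with a written report within 10 business days. No visit is needed for that.

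**Analysis.** SAP 7.4 rules out imputation in general and states: "Subjects who dropped out will be censored at date of last follow-up contact". The decision rule in Protocol 5.0 and SAP 7.7 uses the Kaplan-Meier estimate at day 1095: "If the lower bound is greater than 35%, it will be declared that the PG and the corresponding primary study objective have been met". Neither document plans a sensitivity, tipping-point or worst-case analysis. SAP 7.9 says only that changes made necessary by missing data will be described and justified in the study report.

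**Amount of missing follow-up.** The sample-size text in both documents contains the phrase "Allowing for approximately 30% of subjects lacking a 3-year follow-up visit", and does not split this figure by reason.

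**The concern.** Kaplan-Meier censoring is unbiased only if subjects who leave have the same later risk as those who stay. A subject whose treated segment fails and who is re-treated at another hospital could plausibly drop out of contact for that very reason, and would then be censored as event-free at the last contact.

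In a randomized trial some of this error might cancel between arms. Here one arm is compared with a fixed 35%, so any error passes straight into the decision. Amputation and revascularization leave medical records, so part of the missing information could be recovered without a visit, but the written minimum does not ask for it. The reader of the final report would also have no pre-specified way to see how much the conclusion depends on the assumption.

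**Working it through.** **1. The plan's own figures.** Inputs from Protocol 5.0 and SAP 6: goal 0.35, expected rate 0.55, one-sided alpha 0.025 (1.96), power 90% (1.28).

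- n = 0.35×0.65 × (1.96 + 1.28×√(0.55×0.45 / (0.35×0.65)))² / 0.20² = 61.75, so 62, as stated.
- 62/0.70 = 88.6, so 89, as stated. For the fracture endpoint, 97/0.90 = 107.8, so 108, as stated.
- 48/108 = 44.4%, with lower bound 0.444 − 1.96×√(0.444×0.556/108) = 35.1%, as in Protocol Table 9 and SAP Table 2.

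The sample size is not in question. With 70% of 108 (about 76) evaluable, the plan's formula still gives about 95% power at 55%. The issue is bias, not power.

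**2. Effect of informative loss on the error rate.** Model: N = 108, a fraction f leaves at uniform times over three years, with constant hazard h before leaving and k·h afterwards. h is set so that the true 36-month event-free rate is 35%:

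(1−f)·e^(−h) + f·(e^(−h) − e^(−kh)) / ((k−1)h) = 0.35

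For k = 1 this reduces to e^(−h) = 0.35. Kaplan-Meier estimates e^(−h), the rate without the altered later hazard. For f = 0.30 and k = 2, h = 0.939 and e^(−h) = 39.1%, about 4 points too high. Simulation at f = 0.30 (4,000 runs per cell, plain Greenwood bound):

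| k | Mean estimate | Chance goal declared met |
|---|---|---|
| 1 | 35.1% | 2.4% |
| 1.5 | 37.4% | 6.4% |
| 2 | 39.2% | 12.0% |
| 3 | 41.7% | 24.3% |

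A separate simulation gave 2.3%, 6.5%, 11.5% and 25.9%. Smaller lost fractions, in the same model with 6,000 runs:

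| Lost | k = 2 | k = 3 |
|---|---|---|
| 10% | 4.4% | 5.8% |
| 15% | 5.3% | 9.3% |

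With k = 0.5 and 30% lost, the chance falls to 0.4% and the estimate is about 3 points too low. The documents give no value for k, and the fractions lost are also assumptions.

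**3. Tipping point by observed rate.** Assume 30% leave uniformly and call the Kaplan-Meier rate S.

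- Complete and event-free: C = 108×0.70×S.
- Lost while event-free: L = 108×0.30×(1−S)/(−ln S).
- Share of L expected to have had events if censoring is non-informative: 1 − 32.4×S/L.
- The binomial bound on 108 equals 35% at a rate of 44.37%, or 47.9 subjects event-free. The tipping share is therefore 1 − (47.9 − C)/L.

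| S | C | L | Expected share | Tipping share |
|---|---|---|---|---|
| 48% | 36.3 | 23.0 | 32% | 49% |
| 50% | 37.8 | 23.4 | 31% | 57% |
| 55% | 41.6 | 24.4 | 27% | 74% |

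For example, at 50% observed, if 60% of the 23.4 had events the rate is (37.8 + 0.40×23.4)/108 = 43.7% and the bound is 34.3%.

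**4. A harsher bound.** Suppose all 32 (30% of 108) are lost event-free and only 76 are known. At 42/76 (55.3%) the goal fails once 27 of the 32 (84%) had events, against 14.3 expected. At 36/76 (47.4%), the smallest passing count, it fails at 21 of 32, against 16.8 expected.

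**The case against.** Several stronger readings are tempting, and the documents do not support them.

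- **That tracing stops after three calls and a letter.** It does not. The text presents these steps as a minimum under a duty to make every attempt. That duty is aimed at completing visits, however, not at establishing endpoint status.
- **That endpoint events are captured only at visits.** The Adverse Events and Deaths sections require reports at any time once the site is aware, and Unscheduled Assessments During Follow-up requires data before a target-vessel re-intervention. What remains is events at other providers that the site never learns of. Source verification by monitors covers data already entered and is not a search for such events. The Manual of Operations is not among the documents, so tracing steps written there cannot be ruled out.
- **That 30% is a planned loss rate.** It is a sample-size allowance for lacking a 3-year visit for any reason. It may include subjects who already had an event, deaths after day 30 (not primary events) and withdrawals. It serves here as an upper range.
- **That the error must favour the device.** The documents do not say that lost subjects do worse. Subjects who feel well may also stop attending, and the bias then reverses.

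It is also fair to say that non-informative censoring is the standard Kaplan-Meier assumption, and that at the planned 55% a reversal needs about 70% to 80% of those lost event-free to have had events. That corresponds to a later hazard roughly 4.6 to 7 times higher.

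All of this narrows the point. It does not supply an endpoint check in the tracing minimum or a pre-specified examination of the censoring. The commitment in SAP 7.9 to report later changes is not pre-specification.

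**Conclusion.** The point holds as an improvement the plan should make. The written minimum contains no check for endpoint events, dropouts are censored at last contact, and success is declared from a single bound with no test of the censoring assumption.

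The inflation in step 2 rests on an assumed fraction lost and an assumed hazard ratio after loss, with constant hazards and uniform leaving times. The 12% to 25% range needs both the full 30% lost and a doubled or tripled later hazard.

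The practical exposure is a result near the goal. Around 48% to 50% observed, the conclusion turns if about half to three-fifths of those lost event-free had events, against about a third expected. The plan's own outcome table shows success from 44.4%, so such results are within the range it contemplates. A reader might infer that the primary test is invalid or the trial undersized. Neither follows: with non-informative censoring the error is close to the nominal 2.5%, and the stated sample sizes reproduce.

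**What to change.** 1. **SAP 7.4 and 7.7.** Keep the Kaplan-Meier test as primary. Pre-specify a tipping-point table that assigns events to an increasing share of all subjects censored event-free before day 1095. Report the share at which the one-sided 97.5% lower bound reaches 35%, beside the share expected under non-informative censoring.

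2. **Protocol 4.0, Loss to Follow-Up.** For subjects who have not withdrawn consent, add to the minimum a check of site records and with the treating physician for amputation or target lesion revascularization through day 1095, and of vital status for 30-day death. Apply the same search to every such subject, and record the last date on which endpoint status is known whether or not an event is found.

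3. **Censoring date.** Censor at that recorded date, and report the result with censoring at last direct contact as a sensitivity analysis. This matters because a record search can date an event more easily than it can confirm its absence. Extending follow-up mainly for subjects found to have events would bias the estimate downward.

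The cost is a short protocol addition, some coordinator time and a small addition to the SAP tables. No extra subjects or procedures are needed. The downside is that a result near the goal may have to be reported with a qualification.
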